2.1 Hypothesis

Fermented Wheat Germ Extract (FWGE) has activity against epithelial ovarian cancer (OVCA). FWGE may increase sensitivity to chemotherapy and may decrease side effects related to chemotherapy. FWGE active components (2,6-dimethoxy-p-benzoquinone) may be detected in serum of women receiving FWGE.

In an effort to generate preliminary data to support a future peer-reviewed grant-funded large phase II clinical trial of adjuvant FWGE in women undergoing therapy for ovarian cancer and to test the safety and tolerability of FWGE, we propose a pilot randomized, placebo-controlled study of FWGE in women with a suspected diagnosis of OVCA. We propose to test the safety and tolerability of FWGE, and to determine if we can detect an active product of FWGE (2,6-dimethoxy-p-benzoquinone) in the serum, and whether short-term therapy with FWGE has an effect on the tumor marker, CA125. We will analyze changes in tissue proliferative assays and gene expression in women who receive FWGE (n=10) and those who receive placebo (n=10).

We recognize that the sample size in the current study will prohibit definitive statistical conclusions to be drawn on our primary objective (to test the safety and tolerability of FWGE), or our secondary objectives (to compare levels of FWGE active product, CA125 levels, proliferation, and gene expression in OVCAs from subjects receiving FWGE versus placebo). The study is neither designed nor powered to develop statistically significant results, rather, we seek to develop preliminary/pilot data that will enable us to pursue a future large phase II, peer-reviewed grant-funded trial of adjuvant FWGE in women undergoing therapy for ovarian cancer. Preliminary data developed in the current proposal will support such grant applications.

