the control group. There was a statistically significant improvement in progression-free survival 55.8 months (FWGE) versus 29.9 months (control) p = 0.0137. There was a statistically significant improvement in overall survival of 66.2 months (FWGE) versus 44.7 months (control) p = 0.0298 [17].

3.35 Summary and Rationale:

Fermented wheat germ extract has been demonstrated in vitro to induce ovarian cancer cell growth arrest and apoptosis. When FWGE is combined with cisplatin chemotherapy it enhances cell killing. In animal studies, FWGE has shown no toxicity and anticancer effects. Observations from human clinical trials demonstrate FWGE to be safe and without serious adverse events. The data also suggest beneficial effects of FWGE on disease progression and survival in patients with melanoma and colorectal cancer.

3.4 Proposal Overview: In this pilot clinical trial, we will evaluate the safety, toxicity and quality of life (QoL) of ten women with ovarian cancer scheduled to undergo surgery, administered FWGE versus ten women receiving placebo daily for up to 4 weeks. We hypothesize that FWGE will be safe and non-toxic and that administration may decrease some of the symptomatology associated with ovarian cancer. As secondary objectives, we will seek to determine whether we can detect differences in levels of 2,6-dimethoxyp-benzoquinone (one of FWGE's active products), in the serum of women receiving FWGE versus placebo. We will also evaluate the impact of FWGE on the tumor serum marker CA125, as well as histologic tumor proliferation and gene expression in ovarian cancer. As noted above, we recognize that the sample size in the current study will prohibit definitive statistical conclusions to be drawn on our primary objective (to test the safety and tolerability of FWGE), or our secondary objectives (to compare levels of FWGE active product, CA125 levels, proliferation, and gene expression in OVCAs from subjects receiving FWGE versus placebo). The study is neither designed nor powered to develop statistically significant results, rather, we seek to develop preliminary/pilot data that will enable us to pursue a future large phase II, peer-reviewed grant-funded trial of adjuvant FWGE in women undergoing therapy for ovarian cancer. Preliminary data developed in the current proposal will support such grant applications.

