12.0 STATISTICAL CONSIDERATIONS

12.1 Study Design: This study is a randomized, double-blind, placebo-controlled, trial of the effect of FWGE on women with epithelial ovarian cancer scheduled to undergo surgery. As noted above, we recognize that the sample size in the current study will prohibit definitive statistical conclusions to be drawn on our primary objective (to test the safety and tolerability of FWGE), or our secondary objectives (to compare levels of FWGE active product, CA125 levels, proliferation, and gene expression in OVCAs from subjects receiving FWGE versus placebo). The study is neither designed nor powered to develop statistically significant results, rather, we seek to develop preliminary/pilot data that will enable us to pursue a future large phase II, peer-reviewed grant-funded

trial of adjuvant FWGE in women undergoing therapy for ovarian cancer. Preliminary data developed in the current proposal will support such grant applications.

- 12.2 Primary outcome variable: The principal parameters to be collected, analyzed and reported will be:
- patient and disease characteristics: age, race, co-morbidities, cancer histologic
 type and stage. Optimal versus suboptimal surgical cytoreduction.
 - differences in toxicity
 - differences in quality of life

For each measure, Student's t-test will be used to identify differences between FWGE-versus placebo-treated OVCAs.

- 12.3 Secondary outcome variables for placebo versus FWGE:
- -the presence of 2,6-dimethoxy-p-benzoquinone in the serum
- -the change in the tumor marker CA125,
- -tumor proliferation as measured by Ki-67.

For each measure, Student's t-test will be used to identify differences between FWGEversus placebo-treated OVCAs.

12.4 Secondary outcome variables for genomic changes in ovarian cancer tissue for placebo versus FWGE.

Expression values will be calculated using the robust multi-array average (RMA) algorithm implemented in the Bioconductor (http://www.bioconductor.org) extensions to the R statistical programming environment.

Student's t-test will be used to identify differentially expressed genes in comparisons between FWGE- versus placebo-treated genomic data. Differentially expressed genes will analyzed using GeneGO MetaCore™ software to identify represented biologic pathways.

12.5 Accrual, Sample Size, and Study Duration: The study plan is a one-stage, randomized, double-blind, clinical trial. Patients will be randomized with equal

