probability to receive either FWGE or placebo. The study will accrue 20 patients. It is anticipated that the accrual of this many patients will be achieved in 18 months. Less than 10% of the patients registered are expected to be lost due to follow-up or any other reason, so 20 accruals should allow for 18 evaluable cases.

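### Sections 12.2 and 12.3 name only a t-test for comparing the arms of a pilot not powered for one; no confidence interval is specified, and toxicity has no named summary measure

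*Combined protocol and SAP*

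**What the plan says.** Section 12.2 lists patient and disease characteristics, differences in toxicity and differences in quality of life as the main parameters to be analysed and reported. Section 12.3 lists the presence of 2,6-DMBQ in serum, the change in CA125, and Ki-67. Both close with the same sentence: "For each measure, Student's t-test will be used to identify differences between" the FWGE and placebo groups. No other between-arm method is given for these measures in Section 12.

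Section 12.1 states: "The study is neither designed nor powered to develop statistically significant results". It adds that the sample size rules out definitive conclusions on safety, and that the aim is pilot data for a later phase II trial. The working hypothesis in Section 3.4 is one of no harm: "We hypothesize that FWGE will be safe and non-toxic".

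On size, Section 12.5 says "The study will accrue 20 patients". It allows for losses of under 10% from all causes and arrives at 18 evaluable patients.

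Outside Section 12:
- 6.26 asks for descriptive statistics of baseline FACT-O and a paired t-test of later scores against baseline.
- 6.231 and 9.23 call for a Ki-67 percentage compared by arm.
- 9.21 and 9.22 call for CA125 response and DMBQ presence by arm.

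None of these sections specifies an interval.

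**The concern.** The main question is whether FWGE does harm, and the only named comparison is a test for a difference. In a trial this small, failing to find a difference is weak evidence of safety whichever test is used. The t-test is also an awkward choice for DMBQ presence, which is yes/no, and for toxicity, which has no defined per-patient score.

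What is at stake is the pilot's own product. Planning a phase II trial needs toxicity rates, SDs of change and the uncertainty around both. The plan commits to SDs only for baseline FACT-O and names no toxicity rate. A p-value from a test with disclaimed power supplies none of these, and it does not show a reader which rates of harm remain possible.

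**Working it through.** **Inputs from the plan.** 20 patients (12.5), 10 per arm (2.1, 3.4), equal allocation and up to 10% loss (12.5), Student's t-test (12.2, 12.3).

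**Assumptions.** The plan does not state the following:
- Toxicity is scored yes/no per patient.
- Tests are two-sided at 0.05.
- Losses are balanced, giving 9 per arm.
- The three-patient excess is illustrative.

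**Step 1, the plan's own figure.** 20 × (1 − 0.10) = 18 evaluable, which matches 12.5. Balanced, that is 9 per arm.

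**Step 2, the prescribed test on an observed three-patient excess.** With a and b events in n per arm, the pooled variance is s² = [a(n−a) + b(n−b)] / [n(2n−2)], and t = [(b−a)/n] / √(2s²/n) on 2n−2 degrees of freedom. For 0/10 against 3/10: s² = 21/180 = 0.1167, SE = √(0.2 × 0.1167) = 0.153, t = 0.3/0.153 = 1.96 on 18 df, p = 0.065.

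| Placebo v FWGE, 10 per arm | t-test p | Fisher p | Newcombe 95% CI for the difference (points) |
|---|---|---|---|
| 0 v 3 | 0.065 | 0.21 | -4 to +60 |
| 1 v 4 | 0.135 | 0.30 | -8 to +60 |
| 2 v 5 | 0.177 | 0.35 | -11 to +60 |
| 3 v 6 | 0.196 | 0.37 | -12 to +60 |

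The remaining cases (4 v 7 to 7 v 10) mirror these. With 9 per arm, a three-patient excess gives t-test p = 0.063 to 0.177.

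**Step 3, the interval for 3/10 against 0/10.** The Wilson limits are 0.108 to 0.603 for 3/10 and 0 to 0.278 for 0/10. Newcombe lower limit: 0.3 − √[(0.3−0.108)² + 0.278²] = -0.04. Upper limit: 0.3 + (0.603−0.3) = 0.60.

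**Step 4, what zero events excludes.** The two-sided 95% Clopper-Pearson upper limit is 1 − 0.025^(1/n): 30.8% for n = 10 and 33.6% for n = 9.

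**Step 5, a true 30-point excess.** Both binomials were enumerated exactly for placebo rates from 0% to 50%. The two-sided t-test is significant in 25% to 35% of trials at 10 per arm and in 24% to 31% at 9 per arm. It therefore misses such an excess about 65% to 76% of the time.

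**Step 6, continuous measures.** The 95% interval for a difference in means has half-width t(0.975, 2n−2) × √(2/n) SD: 2.101 × 0.447 = 0.94 SD at 10 per arm, and 2.120 × 0.471 = 1.00 SD at 9 per arm.

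**The case against.** There are four fair points on the plan's side.

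1. **Estimates are not absent.** Section 12.2 says differences in toxicity and quality of life will be reported. Section 6.26 gives baseline FACT-O summaries, 6.231 and 9.23 give Ki-67 percentages by arm, and 9.21 and 9.22 give CA125 response and DMBQ presence by arm. A reader might infer that the plan produces p-values and nothing else; the documents do not support that.

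2. **The significance results rest on unstated inputs.** At one-sided 0.05, 3/10 against 0/10 is significant (p = 0.033). Toxicity is recorded weekly by grade, so the t-test could be run on counts or grades instead. A reader might infer that a 30-point excess is bound to be declared no difference. That does not follow: even at two-sided 0.05, a true excess of that size would be detected in roughly a quarter to a third of trials.

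3. **The plan already urges caution.** Sections 2.1, 3.4 and 12.1 all say that no definitive safety conclusion can be drawn. A reader might infer that 12.1 declares significance impossible, or that the sponsor will call FWGE safe after a null test. Neither is supported. 12.1 speaks of design and power only, and 4/10 against 0/10 gives p = 0.025. Section 3.4 states a hypothesis, not a rule for interpreting results. Sections 8.1 and 11.2 also require graded adverse events and full descriptions of serious ones.

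4. **A pilot should not be judged by power.** This is right, and it is the reason to specify precision instead.

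These points narrow the concern but do not remove it. The caveat in 12.1 says what cannot be concluded; it does not say what will be reported in its place. None of the sections cited supplies an interval or defines how toxicity is to be summarised.

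**Conclusion.** The point holds in a limited form. For the measures in 12.2 and 12.3, the t-test is the only between-arm method Section 12 names, no confidence interval is specified anywhere, and toxicity has no named summary measure. That does not fit a pilot whose question is absence of harm and whose product is planning data.

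Given a yes/no toxicity endpoint and two-sided 0.05, no observed three-patient excess at 10 per arm reaches significance, although the data would be compatible with an excess of about 60 points. Zero events on FWGE would leave true rates of about 31% (10 per arm) to 34% (9 per arm, if losses are balanced) unexcluded. The absence of any interval or toxicity summary does not depend on these assumptions; the p-values do.

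This does not invalidate the trial. It is a change worth making before analysis, because it decides whether the pilot delivers usable rates, SDs and uncertainty.

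**What to change.** Replace the test sentences in 12.2 and 12.3, and the paired t-test in 6.26, with wording along these lines:

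> The primary output is arm-specific estimates and between-arm differences with 95% confidence intervals. Toxicity is the proportion of patients with at least one event of CTCAE grade [to be stated] or higher. For this and for DMBQ presence, Clopper-Pearson intervals are given per arm and Newcombe intervals for the difference. For change from baseline in FACT-O and CA125, and for Ki-67, means, SDs and t-based intervals are given per arm and for the difference. Any p-value is descriptive. A non-significant difference will not be taken as evidence of safety.

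Add to 12.5 that zero events in an arm excludes only true rates above about 31% with 10 patients, or about 34% with 9.

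Changing 6.26 together with Section 12 matters; otherwise quality of life would have two unreconciled analyses. The trial team must choose the toxicity grade threshold, because the proportions cannot be calculated without it.

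Cost: wording only, with no change to sample size, data collection or patient procedures. The downside is that there is no headline p-value, and the stated safety precision looks less favourable.

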6.2 Treatment plan

- 6.21 All subjects will undergo:
 - 6.211 history and physical examination within 28 days of study entry.
 - 6.212 laboratory evaluation: complete blood count, differential, comprehensive metabolic panel and CA125 test prior to starting protocol therapy and preoperatively.
 - 6.213 serum pregnancy test (within 7 days of starting study drug), for women of child-bearing potential.
 - 6.214 Evaluation for National Cancer Institute's Common Toxicity Criteria, all grades at the time of enrollment, then weekly and the day of surgery.
 - 6.215 Quality of life questionnaire (FACT-O) at the time of enrollment, then weekly and the day of surgery (Appendix I).
- 6.22 Patients will be randomized to treatment with either FWGE or placebo and assigned a blinded treatment number corresponding to one of the two treatment groups. The pharmacy will label the appropriate blinded drug specifically for the patient. A daily supply of drug will be given to the patient from the study pharmacy. The amount will be determined by the time until the surgical procedure is scheduled. Neither patients nor treating physicians will be informed of patients "treated/control" status.

Participants will undergo their planned surgery within 4th week after entry into the study. However, if there are delays, patients can continue to take drug/placebo

for a time period no greater than 2 months. If surgery has not occurred after this 2-month period, the patient will be removed from the study.

Participants will take the study drug up until the day prior to surgery. A separate consent form will be obtained for the surgical procedure.

6.23 The primary tumor tissue obtained during the subject's surgery will be transferred to the pathology department for processing.

6.231 Formalin Fixation

Tissue will undergo formalin fixation then embedment in paraffin; tumor tissue will be stained using the H&E process and will be examined by light microscopy. The tumor will also be stained by immunohistochemical (IHC) stain for proliferation marker Ki-67 (Anti-Ki67 primary antibody, catalog number 790-2910, Ventana, Tucson, AZ, USA). The proliferation index will be calculated by percent of nuclear staining of the tumor for tumor tissue treated with FWGE versus placebo and the result will be compared. The reading pathologist will be blinded to the treatment group.

6.232 Fresh frozen

An additional specimen, approximately 30mg, will be flash frozen.

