6.26 Quality of Life (QoL)

Patients receiving FWGE may experience a positive or negative affect on QoL relative to those who receive placebo.

The measures used in this study to assess QoL are the self-administered Functional Assessment of Cancer Therapy questionnaire for ovarian cancer (FACT-O) a 39-question assessment. Patients will be asked to complete these questionnaires at the following time points during their participation in the study:

- At the time of enrollment
- ii. Weekly
- iii. Prior to surgery

Construct and content

The Functional Assessment of Cancer Therapy scale developed for ovarian cancer (FACT-O) is a tool that provides a general QoL score. It consists of 3 subscales: physical well-being (7 items), social/family well-being (7 items), emotional well-being (6 items), functional well-being (7 items), and the Ovarian Cancer subscale (12 items). This questionnaire has been found to be valid and reliable [21].

Descriptive statistics from the baseline QoL data will be calculated. These will include descriptions of the distribution of QoL scores (mean, standard deviation, median, etc.). For all patients the baseline scores will be calculated using the questionnaire completed at the time of enrollment.

Differences in FACT-O scores between patients receiving FWGE and placebo: A paired t-test will be used to test the null hypothesis that there is no difference between baseline PF scores and the PF scores weekly and prior to surgery for those patients randomized to FWGE versus placebo.

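### FACT-O is collected at enrolment in every woman, but neither planned quality-of-life analysis compares the arms with adjustment for it

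*Combined protocol and SAP*

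**What the plan says.** Section 2.21 puts quality of life in the primary objective, and 12.2 lists differences in quality of life among the primary outcome variables. All subjects follow the schedule in 6.215: "Quality of life questionnaire (FACT-O) at the time of enrollment, then weekly and the day of surgery (Appendix I". Section 6.26 defines the baseline: "For all patients the baseline scores will be calculated using the questionnaire completed at the time of enrollment".

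Two analyses are named.

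- **Section 12.2:** "For each measure, Student's t-test will be used to identify differences between FWGE-versus placebo-treated OVCAs". It gives no covariate and no time point, and does not say whether the outcome is a final score or a change.
- **Section 6.26:** under a heading about FACT-O differences between the FWGE and placebo groups, a paired t-test of baseline PF scores against the weekly and pre-surgery PF scores. PF is not defined and is not one of the FACT-O subscales that 6.26 lists.

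No section uses the enrolment score as a covariate in a comparison of arms. On size, section 12.5 says "The study will accrue 20 patients", "so 20 accruals should allow for 18 evaluable cases". Sections 2.1, 3.4 and 12.1 say that the study is not powered and is meant to supply pilot data for a phase II application.

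**The concern.** With about 10 women per arm, the arms can easily differ in FACT-O at entry. A between-arm t-test on final scores passes rho times that gap into the estimated treatment difference. A t-test on change from baseline passes (1 - rho) times the gap in the opposite direction. A linear model with the enrolment score as covariate removes this dependence and, at moderate correlation, also narrows the interval.

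The paired test in 6.26 does use the baseline, but it answers a different question: whether scores moved over time within women. Run separately in each arm, it invites the reader to compare one significant result with one non-significant result, which is not a test of the arm difference.

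At stake is the quality of an estimate intended for planning a later trial. The validity of a confirmatory conclusion is not in question, because the plan seeks none.

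**Working it through.** **Inputs from the plan.** Accrual is 20 women with equal allocation probability (12.5); 10 per arm are expected (2.1); loss is below 10% (12.5). The plan's own figure reproduces: 20 × (1 - 0.10) = 18 evaluable, or about 9 per arm.

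**Assumptions.** The plan states no FACT-O SD, correlation, alpha or effect size. I work in SD units, with equal SD at enrolment and pre-surgery, normal scores, complete data, exactly n per arm, 95% intervals, and rho of 0.3, 0.5 and 0.7.

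**Chance gap at baseline.**
- SE = sqrt(2/n) = sqrt(2/10) = 0.447 SD.
- P(gap of at least 0.5 SD, either direction) = 2 × Phi(-0.5/0.447) = 0.264, about 26%.
- At 9 per arm the SE is 0.471 SD and the chance is about 29%.

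**Variance of the arm difference, relative to a final-score t-test.**
- Change score: 2(1 - rho).
- ANCOVA: (1 - rho²) × [1 + 1/(2n - 4)]. The bracket is the average price of estimating the slope; at n = 10 it is 1 + 1/16 = 1.0625.

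**95% half-widths at rho 0.5, n = 10.**
- Final score: t(18) × sqrt(2/10) = 0.940 SD.
- ANCOVA: t(17) × sqrt(0.75 × 2/10) × sqrt(1.0625) = 0.842 SD.

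| rho | Relative variance: change | Relative variance: ANCOVA | Half-width: final / change / ANCOVA (SD) | Carry-over of a +0.5 SD gap: final / change (SD) |
|---|---|---|---|---|
| 0.3 | 1.40 | 0.91 × 1.0625 = 0.97 | 0.94 / 1.11 / 0.93 | +0.15 / -0.35 |
| 0.5 | 1.00 | 0.75 × 1.0625 = 0.80 | 0.94 / 0.94 / 0.84 | +0.25 / -0.25 |
| 0.7 | 0.60 | 0.51 × 1.0625 = 0.54 | 0.94 / 0.73 / 0.69 | +0.35 / -0.15 |

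**Break-even against a final score.** (1 - rho²) × 1.0625 = 1 gives rho² = 0.059 and rho of about 0.24. At rho 0.2 the relative variance is 0.96 × 1.0625 = 1.02, a slight loss.

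**At 9 per arm** the bracket is 1 + 1/14 = 1.071. The ANCOVA ratios are 0.975, 0.804 and 0.546, and at rho 0.5 the half-width falls from 1.00 to 0.90 SD.

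**Simulation check** (20,000 trials, 10 per arm, rho 0.5). The SD of the estimate was 0.444 (final), 0.445 (change) and 0.397 (ANCOVA); (0.397/0.444)² = 0.80, as the formula gives. The correlation of the estimate with the baseline gap was 0.50, -0.51 and 0.00.

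**Why the paired test is no substitute.** Suppose both arms have the same true change of 0.5 SD and each is tested separately at two-sided 5%. At rho 0.5 the SD of change is sqrt(2 × 0.5) = 1, the noncentrality is 0.5 × sqrt(10) = 1.58 on 9 degrees of freedom, and power is 0.293. Exactly one arm is then significant in 2 × 0.293 × 0.707 = 41% of trials, although the arms do not differ.

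**The case against.** Four arguments can be made for leaving the plan alone.

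- **The t-test is valid.** A reader might infer from the carry-over that the 12.2 analysis is biased. The documents do not support that: allocation is random, so the test is unbiased on average and its interval already allows for chance imbalance. A 0.25 SD shift also lies well inside even the adjusted half-width of 0.84 SD. This stands. The weakness concerns precision, and the estimate given the imbalance that actually occurs.
- **Baseline is not ignored.** Section 6.26 uses it, and 12.2 could mean change scores. Against the second reading, 12.3 speaks of change for CA125 while 12.2 does not for quality of life, but the wording does not settle it. If change is meant, the gain at rho 0.7 is small (0.60 against 0.54). At rho 0.3, however, change scores do markedly worse (1.40 against 0.97), and the carry-over remains with its sign reversed.
- **The gain depends on an unknown correlation.** This stands. Near 0.3 the gain over a final-score test is negligible.
- **It is a pilot.** The plan disclaims definitive conclusions, and the result will be imprecise under any analysis. This limits the importance of the point but does not remove it, since the estimates are what the pilot is meant to deliver.

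**Conclusion.** The point holds as a modest matter of efficiency and consistency. The plan collects the enrolment score in every woman, names two quality-of-life tests that do not agree, and in neither compares the arms with adjustment for that score. At an assumed rho of 0.5 and 10 per arm, adjustment lowers the variance of the arm difference by about 20% and the half-width by about 10% (0.94 to 0.84 SD). The gain is larger at 0.7, negligible at 0.3 and absent below about 0.25. About one trial in four would start with a gap of at least 0.5 SD. All of this rests on the assumed correlation, on normal scores with equal SDs, and on complete data.

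Two stronger readings are tempting and should not be drawn. A reader might take the 25% fall in residual variance (1 - rho² = 0.75) as the gain in the arm comparison; after the cost of estimating the slope it is about 20%. A reader might also infer that the FACT-O SD for planning phase II would be noisier under the t-test. It would not: the SD and the correlation can be estimated from the same data whichever test is used.

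**What to change.** - **Section 12.2:** for quality of life, compare arms on the pre-surgery FACT-O total score by ANCOVA, with the enrolment FACT-O total as covariate. Report the adjusted difference with its 95% confidence interval. Use the same covariate for the weekly scores.
- **Section 6.26:** replace the paired t-test and the undefined PF score with a reference to that analysis. Editing 12.2 alone would leave the two sections in conflict.
- **For phase II planning:** also report the unadjusted SDs by arm and the observed correlation between enrolment and pre-surgery scores.

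The cost is a short edit in two sections and one residual degree of freedom, with no new data or visits. The edit does not resolve the varying interval between enrolment and surgery (up to 4 weeks, or up to 2 months if delayed, under 6.22), so that interval should be reported alongside the result.

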2,6-DMBQ will be determined in human plasma by high-performance liquid chromatography tandem mass spectrometry. The method will be validated per ICH/FDA guidelines and chromatography will be conducted similarly as previously published [20]. Plasma samples will be prepared for chromatographic injections by solid-supported liquid extraction (SLE). Calibration and quality control (QC) samples will be made by adding known amounts of 2,6-DMBQ to blank plasma. All calibration, QC, and unknown patient samples will be prepared in 96 well-plate format. Aliquots of human plasma and an internal standard will be added to a Biotage Isolute ® SLE plate. A non-polar solvent, similar to the previously published method, will be used to extract and elute the 2,6-DMBQ to a collection plate. The eluate will be evaporated under a gentle stream of air and wells will be reconstituted with mobile phase for injection. Samples will be injected into a Thermo Accela/TSQ Quantum LC/MS/MS system (Thermo Scientific, San Jose, CA). Analytes will be separated using a C18 column. Column eluate will enter the mass spectrometer via electrospray ionization and

multiple reactions monitoring (MRM) will be employed for identification and quantitation. Peaks will be detected and integrated utilizing Thermo LC Quan software. Calibration curves will be generated for each run and patient sample concentrations back-calculated from the corresponding regression line.

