9. EVALUATION CRITERIA

The evaluation criteria for this study are primarily safety, toxicity, and QoL. Secondary assessments are disease response based on CA125, apoptosis and tumor proliferation, 2,6 DMBQ serum levels, and molecular changes as indicated below.

9.1 Safety, Toxicity and Quality of Life: will be assessed as reviewed in section 6.

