9.2 Response Criteria

9.21 Evaluation of Biomarkers

Biomarker-based response involves assessing the patient's longitudinal CA125 values. The definition of CA125 response is based on the Gynecologic Cancer Intergroup (GCIG 2005) criteria. CA125 response will be determined and compared between FWGE and placebo treated groups

9.22 2.6-DMBQ determination

2,6 DMBQ serum presence will be determined in FWGE versus placebo-treated groups.

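### The objective is to compare levels of 2,6-DMBQ and the assay gives concentrations, but 9.22 and 12.3 define the outcome as presence, with no limit for calling it present and a t-test to analyse it

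*Combined protocol and SAP*

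**What the plan says.** The documents describe the 2,6-DMBQ outcome in two ways.

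- **As a level.** Section 12.1 gives the secondary objectives as "to compare levels of FWGE active product, CA125 levels, proliferation, and gene expression in OVCAs from subjects receiving FWGE versus placebo", and 2.1 and 3.4 carry the same statement. Section 3.4 adds "we will seek to determine whether we can detect differences in levels of 2,6-dimethoxyp-benzoquinone". The introduction to section 9 lists "2,6 DMBQ serum levels, and molecular changes as indicated below".
- **As presence or detection.** Section 2.1 also proposes "to determine if we can detect an active product of FWGE (2,6-dimethoxy-p-benzoquinone) in the serum". Section 9.22 states "2,6 DMBQ serum presence will be determined in FWGE versus placebo-treated groups". Section 12.3 lists "the presence of 2,6-dimethoxy-p-benzoquinone in the serum" among the secondary outcome variables, and a footnote to the schema uses the same idea.

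The assay in 6.25 is quantitative, with "patient sample concentrations back-calculated from the corresponding regression line". On its performance the plan says only "The method will be validated per ICH/FDA guidelines". It states no limit of detection or quantification, no threshold for calling a sample positive, and no rule for values below a limit. Section 12.3 applies Student's t-test to every measure it lists, this one included. Table 8.1 schedules the 2,6-DMBQ sample on the day of surgery only.

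**The concern.** A concentration and a yes/no result are different variables and need different analyses. The sections that define and analyse the outcome (9.22 and 12.3) use the yes/no form, while the objective and the assay use the quantitative one. A yes/no result depends on where the assay limit falls, and that limit is left open, so the cut-off could be settled after the data are seen. Presence also cannot show how much exposure was achieved, which is useful when the declared purpose of the pilot is preliminary data for a phase II application. No baseline sample is scheduled, so a woman's own background cannot be subtracted. The comparison between arms carries all the information on exposure.

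**Working it through.** **The plan's own figure.** Section 12.5 plans 20 women with less than 10% lost: 20 × (1 − 0.10) = 18 evaluable, as stated, or 9 per arm if losses fall equally. The plan gives no other figure for 2,6-DMBQ: no effect size, variability, significance level or detection rate. Everything below is illustration on assumed inputs.

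**Does the t-test suit presence?** Suppose all 10 FWGE women are positive and a fraction q = k/10 of placebo women are. Coding presence as 0/1, the pooled t statistic on 18 degrees of freedom reduces to t = (1 − q) / √[q(1 − q)/9] = 3√[(1 − q)/q]. The two-sided Fisher p for the same table is 2 × C(10, 10 − k) / C(20, 10 − k), capped at 1.

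| Placebo positive (k of 10) | t | t-test p | Fisher p |
|---|---|---|---|
| 0 | undefined (zero variance) | – | 0.00001 |
| 5 | 3.00 | 0.008 | 2 × 252/15,504 = 0.033 |
| 6 | 2.45 | 0.025 | 2 × 210/4,845 = 0.087 |
| 7 | 1.96 | 0.065 | 2 × 120/1,140 = 0.21 |
| 8 | 1.50 | 0.15 | 2 × 45/190 = 0.47 |
| 10 | undefined (no contrast) | – | 1.0 |

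The t-test cannot be computed in the clearest result (k = 0). For k = 5 to 8 its p-value is three to four times smaller than the exact one. At k = 6 the two fall on opposite sides of 0.05.

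**When does presence work?** With all 10 FWGE women positive, Fisher p stays below 0.05 for 0 to 5 placebo positives out of 10. With 9 per arm it does so up to 4 of 9 (2 × 126/8,568 = 0.029), and 5 of 9 gives 2 × 126/3,060 = 0.082.

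**What does concentration add?** If every FWGE value exceeds every placebo value, the exact two-sided rank-sum p is 2/C(20, 10) = 2/184,756 = 0.00001. That holds whether 0 or 10 placebo women are above the limit. Complete separation is the case most favourable to this analysis.

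**A less extreme case.** Assume log-normal levels, a 3-fold ratio of geometric means, log-SD 0.8, 9 per arm and a two-sided 5% level. The standardised difference is ln 3 / 0.8 = 1.37, and a t-test on fully quantified log concentrations has 78% power. Fisher's test on presence has these powers:

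| Placebo women above the limit | Power on presence |
|---|---|
| 30% | 44% |
| 50% | 32% |
| 70% | 8% |
| 90% | 0.1% |

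With other ratios at the same log-SD, power on levels is 41% (2-fold), 93% (4-fold) and 98% (5-fold), while presence at 90% placebo detection stays near 0.1%. The 78% requires every value to be quantified, so it is a fair comparator only where detection is high. At 30% placebo detection most placebo values would be below the limit and the concentration analysis would lose power too.

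**The case against.** The strongest defence is that presence is loose wording for a quantitative comparison. The t-test in 12.3 compares means, 12.1 and section 9 say levels, and 6.25 produces concentrations that stay reportable under any wording. This has force: a reader might infer that the plan throws the concentrations away, and the documents do not support that. It does not remove the inconsistency, because on this reading the schema, 9.22 and 12.3 name the wrong variable, and on the literal reading 12.3 puts a t-test on a yes/no outcome.

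The second defence is that detection is an aim in its own right under 2.1. This stands, and presence should stay as a supportive measure.

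The third concerns size. Fisher's test appears nowhere in the plan, and with all 10 FWGE women positive it takes at least 6 of 10 placebo positives to lift its p-value above 0.05. A reader might infer that a real exposure difference is likely to be missed. The documents do not support that either. They report no background of 2,6-DMBQ in untreated women, the placebo is rice-based (5.21), and current FWGE users are excluded (4.21). No dietary restriction is stated, so background is neither shown nor ruled out.

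Finally, the study disclaims power and statistical conclusions, and 2.2 does not list 2,6-DMBQ among the formal objectives, although 2.1, 3.4 and 12.1 treat it as secondary. P-values are therefore a weak yardstick for harm. Validation would also normally yield a quantification limit, but nothing in the plan makes that limit the definition of present.

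**Conclusion.** The point holds as an unreconciled outcome definition with an unsuitable test. Presence alone cannot meet the levels objective, it has no stated limit, and a t-test on it is not valid practice with 9 or 10 per arm. One consequence holds whichever test is used: if all women in both arms are above the limit, presence shows no contrast regardless of concentration. How likely that is cannot be judged from the documents. The Fisher p-values and power figures rest on assumed detection rates, ratios and variability, and show only how much information could be lost. With low background and good detection under FWGE, presence separates the arms. This is a secondary measure in an unpowered pilot, so the correction is worth making before analysis but does not threaten the trial.

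**What to change.** In 9.22 and 12.3 (and the schema footnote, for consistency):

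1. Define the outcome as 2,6-DMBQ concentration on the day of surgery.
2. State the validated lower limit of quantification (LLOQ) before unblinding, and rank values below it as tied lowest.
3. Compare arms with an exact rank-sum test in place of the t-test.
4. Report the median and range per arm, written as <LLOQ where that applies. Give a Hodges-Lehmann difference with 95% CI only if few values are below the LLOQ, or with a stated substitution and a sensitivity range. Ranking settles the test, but the estimate depends on what is substituted.
5. Define present as at or above the LLOQ, and report the proportion per arm with an exact CI as a supportive measure for the detection aim in 2.1.

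The cost is a change of wording and slightly more analysis. The assay already yields the concentrations, so no extra sample is needed.
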